1.2 Scientific Justification for Conducting the Trial

The current proposed dosing regimen for FE 999049 in the submitted application in China is based on each woman's serum AMH concentration and her body weight and is a fixed-dose regimen with the daily dose maintained throughout the stimulation period. In contrast, approved rFSH preparations in China have a conventional dosing approach. Based on the current Chinese local clinical practice, Ferring intends to evaluate the use of FE 999049 in a conventional dosing approach i.e. a standard starting dose fixed for the initial days of stimulation, followed by the possibility for subsequent dose adjustments. The present trial will evaluate the efficacy and safety of FE 999049 in a conventional dosing approach in a long GnRH agonist protocol for pituitary downregulation, as this protocol is commonly used in Chinese clinical practice.

1.3 Benefit / Risk Aspects

Benefits

The fertility medication used for downregulation of pituitary hormones, controlled ovarian stimulation, triggering of final follicular maturation, and all trial-related procedures will be provided to the participating subjects free of charge, as Ferring compensates the investigational sites for their expenses. Subjects participating in this trial may benefit by achieving a pregnancy.

Risks

The risks associated with ART treatment, including the risks of controlled ovarian stimulation and clinical and laboratory procedures, are explained to the subjects as part of the counselling prior to starting treatment.

GnRH agonist protocol

GnRH agonist treatment is associated with adverse drug reactions related to hypoestrogenism, such as mild to severe hot flushes and vaginal dryness, ovarian cysts in the initial flare up part of the treatment, and with higher incidence of OHSS compared with the GnRH antagonist treatment, especially in predicted normal to high responders.^{5,8,11} Given the increased risk of excessive response and OHSS with the GnRH agonist protocol, specific safety measures were implemented in this trial. Consequently, only subjects considered appropriate to receive a starting dose equivalent to 150 IU or 225 IU of GONAL-F and subjects with serum AMH concentrations of ≤ 35 pmol/l are to be included, and subjects at risk of excessive response, OHSS, or PCOS are to be excluded. In addition, cycle cancellation withholding hCG triggering is mandatory if ≥ 25 follicles of ≥ 12 mm are observed at end-of-stimulation and embryo transfer cancellation is mandatory if ≥ 20 oocytes are retrieved. Investigators are allowed to cancel the cycle and the embryo transfer if they evaluate that there is excessive ovarian response or increased risk of OHSS.

Gonadotropins

In this trial, controlled ovarian stimulation will be with one of two rFSH preparations: FE 999049 or GONAL-F. Both preparations will be administered subcutaneously.

The most frequently reported adverse drug reactions during treatment with FE 999049 are headache, pelvic discomfort, ovarian hyperstimulation syndrome (OHSS), pelvic pain, nausea, adnexa uteri pain and fatigue.¹ OHSS is an intrinsic risk of the ovarian stimulation. Known gastrointestinal symptoms associated with OHSS include abdominal pain, discomfort, and distension, nausea, vomiting, and diarrhoea. Ovarian torsion and thromboembolic events are known to be rare complications of ovarian stimulation treatment.

GONAL-F is a commercially available rFSH preparation with established safety and efficacy. The most frequent adverse events in relation to use of GONAL-F are as follows: headache, ovarian cysts and injection site reactions (all reported as very common, i.e. $\geq 10\%$) and abdominal pain, abdominal distension, abdominal discomfort, nausea, vomiting, diarrhoea and mild or moderate OHSS including associated symptomatology (all reported as common, i.e. 1% to $< 10\%$).²⁰ The GONAL-F dosing regimen used in this trial is in line with labelling recommendations.

The most serious risk associated with gonadotropin treatment is OHSS. OHSS manifests itself with increasing degrees of severity. Moderate / severe OHSS is associated with marked ovarian enlargement, fluid accumulation and other complications. In patients treated with a GnRH agonist protocol, early OHSS can be prevented by withholding gonadotropins or withholding human chorionic gonadotropin (hCG). Very rare cases of serious allergic reactions have been reported after injection of gonadotropins.

Trial Procedures and Concomitant Fertility Medications

Subjects will undergo standard ART treatment procedures (e.g. ovarian stimulation monitoring by transvaginal ultrasound and blood sampling, oocyte retrieval and transfer) and also receive standard concomitant fertility medication as part of this trial. The transvaginal ultrasound examinations may be associated with mild discomfort and a very rare risk of infection. The blood sampling might be associated with mild discomfort, bruising and a very rare risk of infection. The oocyte retrieval procedure is associated with discomfort and very rarely infections and bleeding. The transfer procedure is associated with mild discomfort and very rarely infections and mild bleeding. The concomitant fertility medications are generally well-tolerated. The most frequent adverse events are similar to those reported for gonadotropins, such as headache, injection site reactions, pelvic pain, abdominal pain, abdominal distension and allergic reactions. Furthermore, vaginal progesterone has been associated with vulvovaginal disorders and uterine spasms (at a frequency of 1-2%), and the GnRH agonist with vaginal bleeding/spotting (>10%). Ovarian cyst formation is also a recognised complication of GnRH agonist use.

Pregnancy-related Events

A serious concern associated with ART cycles is the frequency of multiple pregnancies / births and the related neonatal health problems. The number of embryos transferred will, for each subject, depend on the local regulations and clinical practice. Participation in this trial does not imply transfer of more embryos than what is judged appropriate by the subject, the investigator and local guidelines and/or regulations. The incidence of miscarriage and ectopic pregnancy is higher in women undergoing controlled ovarian stimulation than in women conceiving spontaneously, though the risk of ectopic pregnancy is mainly higher in patients with a history of tubal infertility. Furthermore, the prevalence of congenital malformations after ART may be slightly higher than after spontaneous conceptions; this is thought to be due to differences in parental characteristics (e.g. maternal age and sperm characteristics) and multiple pregnancies.

Benefits / Risks

Participation in this trial is not expected to have a negative influence on the subject's likelihood of achieving an adequate ovarian response compared to normal clinical practice. Furthermore, participation does not imply extra risks for the subjects in comparison to routine controlled ovarian stimulation. In conclusion, the evaluation of benefits and risks indicates that participation in this trial is associated with a favourable benefit-risk ratio.

2 TRIAL OBJECTIVES AND ENDPOINTS

2.1 Objectives

Primary Objective

- To compare FE 999049 at a starting dose of either 10 µg or 15 µg to GONAL-F at a starting dose of either 150 IU or 225 IU in conventional regimens with respect to ovarian response in women undergoing controlled ovarian stimulation in a long GnRH agonist protocol

Secondary Objectives

- To compare the follicular development, endocrine profile and embryo development associated with conventional dosing of FE 999049 and GONAL-F
- To compare the treatment efficiency associated with conventional dosing of FE 999049 and GONAL-F
- To compare the safety profile associated with conventional dosing of FE 999049 and GONAL-F

2.2 Endpoints

Primary Endpoint

- Number of oocytes retrieved

Secondary Endpoints

- Number of follicles (total and by size category) on stimulation day 6 and end-of-stimulation
- Serum concentrations of estradiol and progesterone on stimulation day 6 and end-of-stimulation
- Number of fertilised oocytes and fertilisation rate
- Number of embryos (total and by quality)
- Total gonadotropin dose and number of stimulation days
- Positive βhCG (positive serum βhCG test 13-15 days after transfer) rate
- Clinical pregnancy (at least one gestational sac 5-6 weeks after transfer) rate
- Vital pregnancy (at least one intrauterine gestational sac with fetal heart beat 5-6 weeks after transfer) rate
- Implantation rate (number of gestational sacs 5-6 weeks after transfer divided by number of embryos transferred)
- Ongoing pregnancy (at least one intrauterine viable fetus 10-11 weeks after transfer) rate
- Ongoing implantation rate (number of intrauterine viable fetuses 10-11 weeks after transfer divided by number of embryos transferred)

- Early ovarian hyperstimulation syndrome (OHSS), late OHSS, and total OHSS (all overall and by grade)

Pregnancy Follow-up Endpoints

[figure not shown]
- Live birth rate
- Neonatal health, including minor/major congenital anomalies, at birth and at 4 weeks after birth

3 INVESTIGATIONAL PLAN

3.1 Overall Trial Design

3.1.1 Trial Design Diagram

A diagram illustrating the trial period is shown in [Figure 3-1](#).

Blood collection: For eligibility criteria, confirmation of downregulation (if applicable), endocrine profile and clinical chemistry and haematology parameters, and for βhCG test.

Ultrasound: For confirmation of downregulation and for monitoring during stimulation. Stimulation day 1 assessments may be combined with confirmation of downregulation assessments, if downregulation is confirmed. Monitoring will continue day 6 and thereafter at least every second day. When the leading follicle reaches a diameter of ≥ 15 mm, assessments will be performed daily.

Luteal phase support: Progesterone will be initiated on the day of oocyte retrieval or the day after and continued until clinical pregnancy (will be stopped earlier in case of menses, negative βhCG or pregnancy loss). The investigator may decide to continue luteal phase support up until the ongoing pregnancy visit, according to local practice.

ET: embryo transfer, GnRH: gonadotropin-releasing hormone, OR: oocyte retrieval; US: ultrasound

Figure 3-1 Trial Diagram – Trial Period

3.1.2 Overall Design and Control Methods

Trial Design

This will be a randomised, controlled, assessor-blind, parallel groups, multicentre, non-inferiority trial comparing the ovarian response of FE 999049 and GONAL-F in conventional regimens, using a starting dose of either 10 µg or 15 µg FE 999049 or 150 IU or 225 IU GONAL-F, in women undergoing controlled ovarian stimulation for IVF or ICSI following treatment in a long GnRH agonist protocol. The trial has been designed to demonstrate non-inferiority of FE 999049 versus GONAL-F with the number of oocytes retrieved as the primary endpoint. Secondary endpoints include pharmacodynamic parameters of FSH action as well as efficacy and safety parameters related to controlled ovarian stimulation. Treatment efficiency in terms of gonadotropin use and duration of stimulation will also be evaluated. The assessor-blind design ensures that the investigators and other assessors such as embryologists are blinded to individual treatment allocation. A trial medication delegate will be responsible for all trial medication related issues, both practically at the clinic and in interactions with the subject.

Subjects will be screened within 90 days prior to randomisation for compliance with the inclusion and exclusion criteria. A long GnRH agonist protocol will be used for pituitary downregulation; treatment with GnRH agonist (triptorelin acetate, DECAPEPTYL, Ferring), 0.1 mg/day, will be initiated in the mid-luteal phase (i.e. cycle day 21-24) of the subject's menstrual cycle. A minimum of 10 days with GnRH agonist administration should be ensured prior to confirmation of downregulation, which is defined as fulfilling the following criteria: 1) menstrual bleeding, 2) shed endometrium with a thickness <5 mm observed by transvaginal ultrasound, and 3) no ovarian follicles ≥10 mm (including cysts that cannot be punctured prior to stimulation) observed by transvaginal ultrasound. In case achievement of downregulation is doubtful or it is deemed helpful, serum estradiol is to be measured (<50 pg/mL or 180 pmol/L; local laboratory). Once downregulation is confirmed, randomisation and start of stimulation must occur within 7 days. Treatment with GnRH agonist is to be continued after confirmation of downregulation and throughout the stimulation period. If the subject has not experienced menstrual bleeding at the first assessment of confirmation of downregulation, a urinary pregnancy test is to be performed. If the subject is not pregnant, treatment with GnRH agonist will be continued and subsequent visit(s) for confirmation of downregulation will be scheduled according to local practice. If downregulation is not achieved after 28 days, treatment with GnRH agonist will be stopped and the subject will be discontinued from the trial as a screening failure.

Randomisation will be stratified according to the investigator's assessment of an appropriate starting dose (10 µg FE 999049 / 150 IU GONAL-F or 15 µg FE 999049 / 225 IU GONAL-F). Randomisation to FE 999049 and GONAL-F will be in a 1:1 ratio within each stratum. Subjects randomised to FE 999049 will receive a daily starting dose of 10 µg or 15 µg which will be fixed for the first five stimulation days. Based on the subject's ovarian response, the dose may be increased or decreased by 5 µg, with dose adjustments implemented not more frequently than once every 2 days. The minimum FE 999049 dose is 5 µg and the maximum FE 999049 dose is 20 µg. Subjects randomised to GONAL-F will receive a daily starting dose of 150 IU or 225 IU which will

be fixed for the first five stimulation days. Based on the subject's ovarian response, the dose may be increased or decreased by 75 IU, with dose adjustments implemented not more frequently than once every 2 days. The minimum GONAL-F dose is 75 IU and the maximum GONAL-F dose is 300 IU. Subjects can be treated with rFSH for a maximum of 20 days, and coasting is not allowed.

During stimulation, subjects will be monitored by transvaginal ultrasound on stimulation days 1 and 6 and thereafter at least every second day. When the leading follicle reaches a diameter of ≥ 15 mm, transvaginal ultrasound will be performed daily. Triggering of final follicular maturation with 250 µg hCG (OVIDREL, Merck Serono) will be done as soon as ≥ 3 follicles with a diameter ≥ 17 mm are observed (i.e. on the day or the day after). Triggering can also be done in case 1 or 2 follicles with a diameter ≥ 17 mm are observed and the investigator judges that ≥ 3 follicles with a diameter ≥ 17 mm cannot be reached, and that triggering is preferred instead of cycle cancellation. If there are < 25 follicles with a diameter of ≥ 12 mm, 250 µg hCG will be administered. If there are ≥ 25 follicles with a diameter of ≥ 12 mm, the cycle is to be cancelled (i.e. hCG will be withheld and the subject will not undergo oocyte retrieval). In case of poor ovarian response, defined as the investigator judging that the triggering criterion cannot be reached by day 20, similarly the cycle is to be cancelled. In case of risk of OHSS or any other safety concern by the investigator, the cycle is to be cancelled.

Oocyte retrieval will take place 36h (± 2 h) after triggering of final follicular maturation. All oocytes from follicles with an estimated diameter ≥ 12 mm must be retrieved. The oocytes can be inseminated by IVF or ICSI. Fertilisation will be assessed on day 1 after oocyte retrieval. The number and quality of embryos will be assessed on day 3 after oocyte retrieval. The embryo quality assessment will consist of the following embryo morphology parameters: number of blastomeres, degree of fragmentation, blastomere uniformity and visual signs of multinucleation. A good-quality embryo is defined as an embryo with ≥ 6 blastomeres and $\leq 20\%$ fragmentation without signs of multinucleation, or with cleavage stage classified as compacting / compacted.

For subjects who undergo triggering of final follicular maturation with hCG and have ≥ 20 oocytes retrieved, no transfer of embryos will take place. For subjects who undergo triggering of final follicular maturation with hCG and have < 20 oocytes retrieved, transfer of 1 or 2 embryos will be performed on day 3 after oocyte retrieval. The decision to transfer either 1 or 2 embryos will be based on the subject's wishes and the investigator's recommendation and in accordance with local guidelines and/or regulations. The investigator has the option of cancelling the embryo transfer for medical reasons. The number and quality of transferred embryo(s) will be recorded. Available embryo(s) can be cryopreserved (either on day 3 after oocyte retrieval or after continued culture to blastocyst stage on day 5 or day 6 after oocyte retrieval) and used by the subject after completion of the trial, in accordance with local guidelines and/or regulations.

Luteal phase support with progesterone (CRINONE, Merck Serono or UTROGESTAN, Besins Healthcare) will be initiated on the day of oocyte retrieval or the day after and continued at least until clinical pregnancy (will be stopped earlier in case of menses, negative β hCG or pregnancy loss). Thereafter the investigator may decide to continue luteal phase support up until the ongoing pregnancy visit, according to local practice. A serum β hCG test will be performed 13-15 days after

transfer (local laboratory). Clinical and vital pregnancy will be confirmed by transvaginal ultrasound 5-6 weeks (35-48 days) after transfer, and ongoing pregnancy will be confirmed by transvaginal or abdominal ultrasound 10-11 weeks (70-83 days) after transfer.

Blood samples will be collected throughout the trial for the purpose of evaluating the endocrine profile and clinical chemistry and haematology parameters. AMH, thyroid-stimulating hormone (TSH), and prolactin concentrations will be assessed at screening, whereas estradiol and progesterone concentrations will be assessed on stimulation days 1 and 6 and at end-of-stimulation. Clinical chemistry and haematology parameters will be assessed at screening and at end-of-trial.

Symptoms of OHSS will be recorded, and all OHSS events will be graded according to Golan's classification system. Early OHSS is defined as OHSS with onset ≤ 9 days after triggering of final follicular maturation, and late OHSS is defined as OHSS with onset >9 days after triggering of final follicular maturation.

If trial procedures and/or assessments are to be performed on Sundays, public holidays or outside the opening hours of the clinic, the procedures and/or assessments can be postponed to the upcoming weekday (maximum one day after original visit schedule).

All subjects with an ongoing pregnancy will be followed until delivery for collection of information on pregnancy outcome. Data on neonatal health, including any congenital anomalies, at birth and at 4 weeks after birth will be collected and reported separately.

3.1.3 Trial Schedule

First patient first visit (FPFV): Q2 2024
Last patient last visit (LPLV): Q4 2025
Pregnancy follow-up completed: Q2 2026

3.2 Planned Number of Trial Sites and Subjects

An approximate number of 300 subjects is planned for randomisation (150 subjects to treatment with FE 999049 and 150 subjects to treatment with GONAL-F) at 10-15 sites in China.

3.3 Interim Analysis

No interim analysis is planned.

3.4 Data Monitoring Committee

No Data Monitoring Committee will be established for this trial. During the trial, the Safety Management Team at the sponsor will evaluate blinded safety data on a regular basis.

3.5 Discussion of Overall Trial Design and Choice of Control Groups

3.5.1 Trial Design

The primary objective of the trial is to compare FE 999049 at a starting dose of either 10 µg or 15 µg to GONAL-F at a starting dose of either 150 IU or 225 IU in conventional regimens with respect to ovarian response in women undergoing controlled ovarian stimulation in a long GnRH agonist protocol. In China, approved rFSH preparations such as follitropin alfa (GONAL-F) and follitropin beta (PUREGON/FOLLISTIM) have a conventional dosing approach, i.e. fixed starting dose for initial days of stimulation followed by possibilities for subsequent dose adjustments. In contrast, the dosing regimen proposed in the submitted application for FE 999049 in China is based on each woman's serum AMH concentration and her body weight using a GnRH antagonist protocol. The dose selection is further discussed in Section 3.5.4.

A long GnRH agonist protocol is commonly used in Chinese clinical practice and therefore that downregulation protocol will be applied in the current trial. The majority of clinical trial data with FE 999049 has been generated in a GnRH antagonist protocol. Data from a phase 3b trial conducted in EU (Trial 000304), showed that number of oocytes retrieved after controlled ovarian stimulation using an individualised FE 999049 dosing regimen based on serum AMH concentrations and body weight of women, with serum AMH concentrations of ≤ 35 pmol/L, was higher with the long GnRH agonist protocol compared to the GnRH antagonist protocol, with a difference of 1.31 [95% CI: 0.22; 2.40]. The number of oocytes retrieved was influenced by age and serum AMH concentration, and the difference between the protocols was largest for younger patients and for patients with higher ovarian reserve. No differences in incidence of OHSS or in the overall safety profile were observed between the protocols. After controlled ovarian stimulation using the individualised FE 999049 dosing regimen, live birth rate and neonatal health follow-up data collected up to 4 weeks after birth were similar for the two protocols. For reassurance of neonatal health data after controlled ovarian stimulation using the conventional FE 999049 dosing regimen with the GnRH agonist protocol, neonatal health data will be collected up to 4 weeks after birth as follow-up to the current trial.

The current trial is randomised and controlled using an approved gonadotropin preparation as active comparator. It is a parallel group design restricted to a single treatment cycle. The trial will be assessor-blind. A double-blind design is not considered feasible for the present trial for various practical reasons, which are described in detail in Section 3.5.3. The assessor-blinding will ensure blinding and thereby unbiased evaluation by the investigators and other assessors such as embryologists. Similarly, Ferring staff will also remain blinded to individual subject treatment allocation during the conduct of the trial (delegated functions that need access to treatment allocation to fulfil their responsibilities are exempted). The trial will be multicentre. This set-up ensures that the required number of subjects can be recruited within a reasonable time and also has the advantage that it should facilitate subsequent generalisation of the results. The selected population, expected to be representative for patients undergoing controlled ovarian stimulation in IVF or ICSI cycles, is further discussed in Section 3.5.5.

This trial is designed to demonstrate non-inferiority of FE 999049 vs. GONAL-F with respect to the number of oocytes retrieved. The non-inferiority margin has been set to 3.00 oocytes, as this margin is regarded to be appropriate for demonstrating the efficacy of FE 999049 treatment in a conventional dosing regimen with a long GnRH agonist protocol. The margin of 3.00 oocytes is in line with the regulatory precedence in Europe for rFSH biosimilars,²¹ and is also a common clinical standard for clinical trials in China demonstrating equivalence between rFSH drug and comparator, e.g. GONAL-F to obtain regulatory approval from the National Medical Products Administration (NMPA).^{22,23,24} Furthermore, the mean number of oocytes retrieved with placebo (i.e. without stimulation) would be approximately 1, and the expected mean number of oocytes retrieved expected with GONAL-F (active control drug) will be approximately 10. Therefore, the efficacy difference between the active control and placebo would be approximately 9, implying that the M1 (defined in the regulatory guideline for clinical non-inferiority trials in China)²⁵ is considerably larger than 3.00. A successful non-inferiority result will therefore both ensure that the effect of FE 999049 is better than placebo and clinically equivalent to GONAL-F, according to regulatory precedence for rFSH biosimilars in Europe and China.^{22,23,24,26,27} Selection of endpoints is further discussed in Section 3.5.2.

Strict criteria have been incorporated in the design of this comparative trial to properly assess the effect of the interventions on treatment outcome. In general, standardisation of criteria, timing of assessments, procedures and interventions have to a great extent been incorporated in the design of this trial to minimise variation.^{28,29,30}

For safety reasons, only subjects with serum AMH concentrations of ≤ 35 pmol/L at screening are eligible for randomisation to treatment and treatment is limited by maximum doses of 20 μ g FE 999049 and 300 IU GONAL-F for a maximum of 20 days. Additional safety measures include cycle cancellation for subjects with ≥ 25 follicles with a diameter ≥ 12 mm or for safety concerns, as judged by the investigator, and transfer cancellation for subjects with retrieval of ≥ 20 oocytes.

Oocytes will be inseminated by either IVF or ICSI reflecting the procedures used in the target population for the proposed indication. Embryos will be cultured for 3 days; oocyte fertilisation will be assessed on day 1 and number and quality of embryos will be assessed on day 3 after oocyte retrieval. The duration of culture in this trial is adapted to clinical practice in China where transfer on day 3 after oocyte retrieval is the most common.

To minimise the risk of multiple gestations, subjects will have transfer of 1 or 2 embryos of the highest quality available. The decision to transfer either 1 or 2 embryos on day 3 will be based on the subject's wishes and the investigator's recommendation and in accordance with local guidelines and/or regulations.

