UTROGESTAN ^{a)} / progesterone	Capsule for vaginal administration	200 mg, three times daily dose

a) UTROGESTAN may be used as an alternative to CRINONE. All subjects included in the trial will be treated with the same progesterone product.

DURATION OF TREATMENT

Subjects can be treated with FE 999049 or GONAL-F for a maximum of 20 days.

STATISTICAL METHODS

Sample Size Justification

In a previous trial (000145) comparing individualised dosing of FE 999049 with GONAL-F in a GnRH antagonist protocol, the standard deviation for number of oocytes retrieved in subjects from China receiving a starting dose of 150 IU of GONAL-F was 7.5. Assuming the standard deviation in this trial to be 7.5, and assuming the treatments to be equally effective for the primary endpoint (number of oocytes retrieved), a sample size of 133 subjects per treatment group will give 90% power to demonstrate non-inferiority of FE 999049 vs. GONAL-F. This is based on a non-inferiority margin of -3.00 oocytes, a one-sided 2.5% significance level, and was calculated using the normal approximation. A total of 300 subjects will be randomised in the trial to ensure at least 90% power also for the analysis of the per-protocol analysis set.

Primary Analysis

The non-inferiority comparison will be performed both for the full analysis set (including all randomised and exposed subjects; analysed as randomised) and the per-protocol analysis set (excluding subjects with major protocol deviations; analysed as treated). The primary endpoint, number of oocytes retrieved, will be compared between FE 999049 and GONAL-F using a negative binomial model with treatment and dose level (10 µg/150 IU or 15 µg/225 IU) as factors. The absolute treatment difference in number of oocytes retrieved and the associated two-sided 95% confidence interval will be derived from the model estimates using the delta method. Non-inferiority will be considered confirmed if the lower limit of the 95% confidence interval for the difference between FE 999049 and GONAL-F is greater or equal than -3.00.

TABLE OF CONTENTS

SYNOPSIS	2
TABLE OF CONTENTS	11
LIST OF TABLES	15
LIST OF FIGURES	15
LIST OF ABBREVIATIONS AND DEFINITION OF TERMS	16
1 INTRODUCTION	18
1.1 Background.....	18
1.2 Scientific Justification for Conducting the Trial.....	19
1.3 Benefit / Risk Aspects	19
2 TRIAL OBJECTIVES AND ENDPOINTS	22
2.1 Objectives	22
2.2 Endpoints	22
3 INVESTIGATIONAL PLAN	24
3.1 Overall Trial Design	24
3.1.1 Trial Design Diagram.....	24

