3.5.2 Selection of Endpoints

The present trial has been designed as a non-inferiority trial with number of oocytes retrieved as the primary endpoint reflecting the pharmacological effect of FSH on follicular development and growth. Known pharmacological effects of FSH are associated with risks of developing OHSS.

Oocytes retrieved is commonly used as primary endpoint for this kind of drugs. The set of secondary endpoints is considered appropriate for an efficacy trial and includes items of special interest related to controlled ovarian stimulation. Safety will be closely monitored and the frequency of OHSS (early, late, and total) is included.

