9 STATISTICAL METHODS

9.1 Determination of Sample Size

In a previous trial (000145) comparing individualised dosing of FE 999049 with GONAL-F in a GnRH antagonist protocol, the standard deviation for number of oocytes retrieved in subjects from China receiving a starting dose of 150 IU of GONAL-F was 7.5. Assuming the standard deviation in this trial to be 7.5, and assuming the treatments to be equally effective for the primary endpoint (number of oocytes retrieved), a sample size of 133 subjects per treatment group will give 90% power to demonstrate non-inferiority of FE 999049 vs. GONAL-F. This is based on a non-inferiority margin of 3.00 oocytes, a one-sided 2.5% significance level, and was calculated using the normal approximation. A total of 300 subjects will be randomised in the trial to ensure at least 90% power also for the analysis of the per-protocol analysis set.

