9.6.2 Primary Endpoint

The primary endpoint, number of oocytes retrieved, will be compared between FE 999049 and GONAL-F using a negative binomial model with treatment and dose level (10 µg/150 IU or 15 µg/225 IU) as factors. The absolute treatment difference in number of oocytes retrieved and the associated two-sided 95% confidence interval will be derived from the model estimates using the delta method. Non-inferiority will be considered confirmed if the lower limit of the 95% confidence interval for the difference between FE 999049 and GONAL-F is greater or equal than -3.00.

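### Does the remark in Section 3.5.1 that success will show clinical equivalence to GONAL-F call for a change, given that the only success rule is a lower limit?

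*Combined protocol and SAP*

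**What the plan says.** Section 3.5.1 opens its margin discussion by describing the trial as a non-inferiority design with a margin of 3.00 oocytes. It supports that figure with European biosimilar precedent and calls it a "common clinical standard for clinical trials in China demonstrating equivalence between rFSH drug and comparator". It then argues from approximate means of 10 oocytes with GONAL-F and 1 without stimulation that the control effect is about 9, well above 3.00. The closing sentence concludes: "A successful non-inferiority result will therefore both ensure that the effect of FE 999049 is better than placebo and clinically equivalent to GONAL-F". The full claim carries a qualifier: "clinically equivalent to GONAL-F, according to regulatory precedence for rFSH biosimilars in Europe and China".

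The operative sections are narrower:

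- Section 9.6.2 declares non-inferiority if the "lower limit of the 95% confidence interval for the difference between FE 999049 and GONAL-F is greater or equal than -3.00". The synopsis gives the same rule: "Non-inferiority will be considered confirmed if the lower limit of the 95% confidence interval for the difference between FE 999049 and GONAL-F" is at or above that value.
- Section 9.1, on sample size: "This is based on a non-inferiority margin of 3.00 oocytes, a one-sided 2.5% significance level".
- Section 3.5.2: "The present trial has been designed as a non-inferiority trial with number of oocytes retrieved as the primary endpoint".
- Section 9.6.1 applies the non-inferiority comparison to both the full analysis set and the per-protocol set.

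A two-sided 95% interval is to be derived, so an upper limit will exist, but no section attaches a criterion to it.

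**The concern.** Equivalence needs a bound on each side. A rule that looks only at the lower limit is met by any sufficiently high result, including one where FE 999049 yields clearly more oocytes than GONAL-F. Taken literally, Section 3.5.1 would label such a result clinically equivalent.

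The upper side has clinical content here. Section 3.5.2 links the pharmacological effect of FSH to the risk of OHSS. Section 3.5.4 says that the match between 15 µg and 225 IU is extrapolated, and that a 15 µg starting dose has not been evaluated in the Chinese population. If the sentence were read as the prespecified meaning of success, a report or submission could claim more than the trial tested.

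**Working it through.** **Inputs.** SD 7.5, margin 3.00, one-sided 2.5%, true difference 0, 90% power and 133 per group (Section 9.1); 150 per arm randomised (Section 3.2); lower-limit rule (Section 9.6.2). The normal approximation is used throughout, as in Section 9.1, and not the planned negative binomial model.

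**1. The plan's own figure.** n per arm = 2 × [7.5 × (1.960 + 1.282) / 3.00]² = 131.3, so 132. With the t distribution, power is 89.9% at 132 and 90.1% at 133. The stated 133 is therefore reproduced to within one subject. Only the lower margin enters the calculation, so the trial was sized for non-inferiority and nothing else.

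**2. What the rule requires.** With 150 per arm, SE = 7.5 × √(2/150) = 0.866, and the half-width is 1.96 × 0.866 = 1.70. The rule is met when the observed difference is at least -3.00 + 1.70 = -1.30, with no ceiling. With 133 per arm, SE = 0.920, the half-width is 1.80 and the threshold is -1.20.

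**3. How far that is from equivalence.** The plan gives no upper limit. Assume, for illustration only, that the whole 95% interval must lie within ±3.00. With true difference d:

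- P(non-inferior) = Φ((d + 3)/SE - 1.96)
- P(equivalent) = Φ((3 - d)/SE - 1.96) - Φ((-3 - d)/SE + 1.96)

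| True difference, 150 per arm | Rule met | Equivalent within ±3.00 | Rule met, not equivalent |
|---|---|---|---|
| 0 | 93.4% | 86.7% | 6.6% |
| +1 | 99.6% | 63.3% | 36.3% |
| +2 | 99.99% | 21.0% | 79.0% |

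With 133 per arm and d = 0, equivalence power would be 80.7%. Reaching 90% would take 163 per arm. The two conclusions are therefore distinct, even under the plan's own assumption of equal effect.

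**4. Does the other half of the sentence hold?** On the plan's approximate means, a loss of no more than 3.00 from 10 leaves 7, which is 6 above the unstimulated value of 1. The margin argument does support superiority to placebo. Only the equivalence half goes too far.

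**5. Where the phrase has effect.** Set against Section 3.1.2 (design), the opening of the margin paragraph in 3.5.1, Section 3.5.2 (endpoints), Section 9.1 (size), Section 9.6.1 (analysis sets), Section 9.6.2 (decision) and the synopsis, the equivalence claim appears only in the rationale sentence. No test, alpha, analysis set or reporting rule refers to it. Removing it leaves every figure in steps 1 and 2 unchanged.

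**The case for a change.** The strongest case for acting is that the sentence is plainly wrong as written. Its verb promises certainty, it sits in a margin justification that cites regulators, and non-inferiority and equivalence support different claims there. The appeal to precedent does not repair it, because the same paragraph describes the Chinese precedent as trials showing equivalence, while this trial uses 3.00 on the lower side only. Nor is an upper bound supplied by cancelling cycles with 25 or more follicles of at least 12 mm and counting them as zero oocytes (Sections 3.1.2 and 9.6.1). That lowers an arm's mean but does not limit the difference between arms.

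All of this stands as criticism of the wording, but three things limit its weight:

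- The sentence closes an argument about how much control effect is preserved. There, clinical equivalence can be read as no clinically relevant loss against the control, which is what the rule does test.
- Over-response is examined elsewhere. OHSS, early, late and total and by grade, is a secondary endpoint, and transfer is withheld when 20 or more oocytes are retrieved. The two-sided interval would also show a difference lying wholly above zero.
- A large upward difference is not what the plan's data suggest. Section 3.5.4 puts the dose matching 150 IU at 10.0 µg (95% CI 9.2 to 10.8), and at 10.2 µg (9.3 to 11.2) in Chinese patients. These estimates bear on 10 µg directly and on 15 µg only by extrapolation.

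**Conclusion.** The observation is correct, but no change to the plan follows. One sentence of rationale overstates what success would show, while every section that governs the trial's conduct and conclusion already limits it to non-inferiority. A statistician applying Section 9.6.2 would report non-inferiority, or the failure to show it, and would find no rule permitting an equivalence claim.

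An edit would have no effect on the estimate, type I error, power (93.4% at 150 per arm under the plan's assumptions), sample size, conduct or safety. The 6.6%, 36.3% and 79.0% figures describe the gap between two kinds of claim under an assumed ±3.00 range. They are not an error rate of this trial.

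The conclusion rests on two conditions: that the sentence is background and not a reporting rule, which is how the protocol uses it, and that the separate statistical analysis plan announced in Section 9.6.1 adds no equivalence conclusion based on the lower limit alone.
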